#### 9.2.3.4. Unscheduled Visits

All attempts should be made to keep a patient on the study schedule. Unscheduled visits may be necessary to repeat testing following abnormal laboratory results, follow-up on adverse events or for other reasons, as warranted. Procedures that may be performed at the Unscheduled visit are as follows:

- Vital signs
- Physical exam
- Skin/ulcer exam
- 12-lead ECG
- Blood and/or urine collection for safety testing.

### 9.2.4. Schedule of Events

Table 2 provides detail on the schedule of assessments.

Table 2: Schedule of Events (Study PCS499-NL01)

Procedure	Screening	Dosing	Visit 3	Visit 4	Visit 5	Visit 6	Visit 7	Visit 8	Visit 9	Visit 10	Extension P	eriod
	(-28 to -1 days)	Visit 2 Day 0 (Baseline Visit)	Week 1 Day 7 (±1 day)	Week 2 Day 14 (±1 day)	Month 1 Day 28 (±3 days)	Month 2 Day 60 (±7 days)	Month 3 Day 90 (±7 days)	Month 4 Day 120 (±7 days)	Month 5 Day 150 (±7 days)	Month 6 Day 180 (±7 days)	Visit 11 Month 9 Day 270 (±10 days)	Visit 12 Month 12/ET Day 360 (±10 days)
PI/informed consent	•											
Demographic information	•											
Medical history	•											
Inclusion/ exclusion criteria	•	•										
Screening Laboratory Testing (Hep B/C, HIV, TB)	•											
Skin biopsy*	•*											
Medications	•	•	2	2	•	•	•	•	•	•	•	•
Vital signs	•	•			•	•	•	•	•	•	•	•
Physical exam	•	•					•			•	•	•
Skin/ulcer exam	•	•			•	•	•	•	•	•	•	•
Photograph/ 3D scan	•	•			•	•	•	•	•	•	•	•
IGA:NL	•	•			•	•	•	•	•	•	•	•
NLCUS		•			•	•	•	•	•	•	•	•
PGA		•			•	•	•	•	•	•	•	•

Protocol PCS499-NL01 Date: 02 November 2018

TIOLOCOLI CDT,	7 7 1 12 0 1								Bate.	02 110 (011)	2010	
DLQI		•			•	•	•	•	•	•	•	•
Skindex-29		•			•	•	•	•	•	•	•	•
PtGA		•			•	•	•	•	•	•	•	•
Safety check- in			*	**								
Safety Laboratory testing***	•	•			•	•	•	•	•	•	•	•
Blood for biomarkers		•			•		•			•	•	•
Pregnancy test**	•	•			•	•	•	•	•	•	•	•
ECG	•	•			•		•			•	•	•
Adverse Events	•	•	*	** **********************************	•	•	•	•	•	•	•	•
Drug Accountability					•	•	•	•	•	•	•	•
Study Drug Dispensed		•			•	•	•	•	•	•	•	
Study Drug Instructions	•	•										

\*If no previous history of biopsy, no biopsy within the previous 5 years, a biopsy that is not confirmed to be NL, or newly active lesion.

\*\*For WOCBP: Serum β-HCG at Screening; Urine pregnancy test at subsequent visits.

\*\*\* Additional hematology (PT, aPTT and INR) will be tested at every visit except Screening. HbA1c will be tested at Day 0 and Months 3, 6, 9 and 12.

## 9.3. Number of Subjects

The number of subjects estimated for this study is  $\sim$ 12 patients (6-9 patients without ulceration and 3-6 patients with ulceration) with Necrobiosis Lipoidica.

Date: 02 November 2018

### 9.4. Treatment Assignment

This is an open label study where the  $\sim$ 12 patients with Necrobiosis Lipoidica will receive PCS499 900mg BID (3 x 300mg tablets) with food.

10.

## SELECTION AND WITHDRAWAL OF PATIENTS

Date: 02 November 2018

This section describes the inclusion and exclusion criteria for entry into the study, as well as patient withdrawal criteria for patients who are enrolled into the study. Any exceptions to these inclusion or exclusion criteria for eligibility require approval of the Medical Monitor in advance.

#### 10.1. Patient Inclusion Criteria

To participate in the study, patients must meet all the following inclusion criteria at screening:

- 1. Male or female patients age 18 to 80 years of age, inclusive, at Screening.
- 2. Biopsy-confirmed diagnosis of NL. Biopsies of continually active lesions performed outside of this clinical study will need to be reviewed and the diagnosis confirmed by the study pathologist. For patients with no previous history of biopsy, no biopsy within the previous 5 years, a biopsy that is not confirmed to be NL, or newly active lesion, a biopsy to confirm a diagnosis of NL will be performed at the Screening visit.
- 3. Reference NL lesion with a score of 2 or greater on the IGA:NL Activity scale AND surface area with minimum size of 10 cm^2. If more than one lesion is present, the reference lesion area is the lesion with the highest disease severity.
- 4. Women of childbearing potential must have a negative serum pregnancy test at the Screening Visit and a negative urine pregnancy test at Baseline before dosing.
- 5. Women of childbearing potential must use one of the following acceptable methods of contraception throughout the study: oral contraceptive medication, intrauterine device (IUD), hormonal implants, injectable contraceptive medications, double-barrier methods, or tubal ligation.
- 6. Females who are postmenopausal (age-related amenorrhea >= 12 consecutive months and increased follicle-stimulating hormone [FSH] > 40 mIU/mL. If necessary to confirm postmenopausal status, an FSH will be drawn at Screening) or who have undergone hysterectomy or bilateral oophorectomy are exempt from pregnancy testing.
- 7. Male patients must be willing to use appropriate contraceptive measures and refrain from sexual activity with any female who is pregnant or lactating.
- 8. Patient must be willing and able to swallow whole tablets.
- 9. Patient must be willing and able to comply with study procedures.
- 10. Patient must be willing and able to provide signed, informed consent.

### 10.2. Patient Exclusion Criteria

Patients will not be eligible for entry into this study if they meet any of the following exclusion criteria:

- 1. Current or previous (within 4 weeks of Baseline) treatment with:
  - a. Oral, topical, or intralesional corticosteroids;

- Date: 02 November 2018
- b. Systemic pentoxifylline, theophylline, or cilostazol
- c. Oral or topical retinoid;
- d. Other systemic or topical immunosuppressant drugs, including but not limited to calcineurin inhibitors (e.g., tacrolimus), thalidomide, apremilast, anti-malarials (e.g., hydroxychloroquine, chloroquine), cyclosporine, mycophenolate mofetil, azathioprine, methotrexate, etc.
- 2. Current or previous (within 12 weeks of Baseline) treatment with any biologic therapy (e.g., adalimumab, etanercept, infliximab, anakinra, etc.).
- 3. Phototherapy/photochemotherapy (NBUVB, UVB, PUVA) within 6 weeks prior to Baseline
- 4. Skin grafting, or other surgical procedure (other than debridement) within 6 weeks prior to Baseline.
- 5. History of drug allergy, including but not limited to pentoxifylline or other xanthine derivatives, or other allergy, which in the opinion of the Investigator, contraindicates participation.
- 6. Anticipated concurrent use of a strong CYP1A2 inhibiting drug, including but not limited to cimetidine and/or fluvoxamine, during the course of the study (after Screening).
- 7. Fever (>38°C), or chronic, persistent, or recurring infection(s) at Screening or Baseline.
- 8. Any infection requiring oral antimicrobial therapy within 2 weeks prior to Baseline or any infection requiring parenteral antibiotics or hospitalization within 12 weeks prior to Baseline. Any treatment for such infections must have been completed and the infection cured for at least 2 weeks prior to Baseline.
- 9. History of sarcoidosis, pyoderma gangrenosum, or any other disorder (in the judgment of the Investigator) that would interfere with the evaluation of NL or require protocol prohibited medication.
- 10. History of any life threatening infection or sepsis within 12 months of Baseline:
- 11. Clinically significant cardiac disease including but not limited to unstable angina, acute myocardial infarction within 6 months of Baseline, and arrhythmia requiring therapy.
- 12. Patient has QTc interval ≥ 480 milliseconds on Screening ECG; a second Screening ECG may be done at investigator's discretion but the average of the two QTc screening intervals must not be ≥ 480 milliseconds.
- 13. History of cerebral hemorrhage, cerebrovascular accident, transient ischemic attack, gastrointestinal bleeding, or retinal hemorrhage within 6 months of Baseline.
- 14. Patient has active or history of neoplastic disease (except for adequately treated non-invasive basal cell and/or squamous cell carcinoma or carcinoma in situ of the cervix) within the past 5 years prior to Baseline.
- 15. Presence of clinically significant medical condition(s) including but not limited to: renal, hepatic, cardiovascular, hematological, gastrointestinal, endocrine, pulmonary, neurological, psychiatric, substance abuse, and/or any other clinically significant disease

- or disorder, which in the opinion of the Investigator (by its nature or by being inadequately controlled), may put the patient at risk due to participation in the study, influence the results of the study, and/or affect the patient's ability to complete the study.
- 16. History of or current diagnosis of active tuberculosis (TB); undergoing treatment for latent TB infection (LTBI); untreated LTBI (as determined by documented results within 3 months of the Screening Visit of a positive TB skin test with purified protein derivative with induration >= 5 millimeter (mm), or a positive QuantiFERON-TB test or positive or borderline T-Spot [Elispot] test); or positive TB test at Screening. Subjects with documented completion of appropriate LTBI treatment would not be excluded and are not required to be tested.
- 17. Vaccination with live or live-attenuated virus vaccine within 1 month prior to Baseline.
- 18. The results of the following laboratory tests performed at the central laboratory at Screening meet any of the criteria below:
  - a. Hemoglobin < 8.0 g/dL (International System of Units (SI): < 80 g/L);
  - b. White blood cells  $< 3.0 \times 10^3$  cells/mm^3 (SI:  $< 3.0 \times 10^9$  cells/L);
  - c. Neutrophils  $< 1.0 \times 10^3 \text{ cells/mm}^3 \text{ (SI: } < 1.0 \times 10^9 \text{ cells/L});$
  - d. Lymphocytes  $< 0.5 \times 10^3 \text{ cells/mm}^3 \text{ (SI: } < 0.5 \times 10^9 \text{ cells/L});$
  - e. Platelets  $< 100 \text{ x } 10^3 \text{ cells/mm}^3 \text{ (SI: } < 100 \text{ x } 10^9 \text{ cells/L})$
  - f. Alanine aminotransferase (ALT), aspartate aminotransferase (AST), and/or alkaline phosphatase (ALP)  $\geq 2$  x upper limit of normal (ULN);
  - g. Total bilirubin level  $\geq 2$  x ULN unless the individual has been diagnosed with Gilbert's disease and this is clearly documented;
  - h. Estimated glomerular filtration rate < 40 mL/min/1.73 m^2 based on the Modification of Diet in Renal Disease (MDRD) formula.
  - i. Positive HIV serology
  - j. Evidence of active Hepatitis B Virus (HBV) infection
  - k. Evidence of active Hepatitis C Virus (HCV) infection
- 19. Women who are pregnant or breastfeeding.
- 20. Patient unwilling or unable to swallow tablets whole.
- 21. Any other medical condition, serious intercurrent illness, or extenuating circumstance that, in the opinion of the Investigator, would preclude participation in the study.
- 22. Use of any investigational product within 30 days prior to Baseline or currently enrolled in another study that involves clinical investigations.

#### 10.3. Patient Withdrawal Criteria

The intent of this study is to follow all subjects until study termination unless the subject withdraws consent. Patients will be informed that they have the right to withdraw from the study

at any time for any reason without prejudice to their medical care. The Investigator also has the right to withdraw patients from the study if it is in their best interest. Patients may be withdrawn from the study if they:

- Have entered the study in violation of the protocol
- Require use of a prohibited concomitant medication
- Experience an AE that warrants premature withdrawal

All treated patients should be followed according to the Schedule of Assessments. All patients, even those who are withdrawn prematurely, should have all evaluations for the Month 12/ET Visit performed, if possible. All procedures required should be documented in the electronic case report form (eCRF). For all patients who withdraw prematurely, the Investigator will indicate one of the following reasons for withdrawal on the eCRF:

- Adverse event (AE)
- Death
- Protocol violation
- Lost to follow-up
- Patient's decision
- Other (reason to be specified by the Investigator)

In case of patients' withdrawal from the study due to an AE, such patients will be closely monitored until the resolution or stabilization of the AE. The Investigator should document the reason for withdrawal in the source documentation and eCRF.

If a patient withdraws participation from the trial early, early withdrawal should be documented by the Investigator (or designee) in the appropriate eCRF pages and source documents when confirmed.

### 11. TREATMENT OF PATIENTS

### 11.1. Description of Study Drug

PCS499 is a stable, optically active, white-crystalline solid with the chemical name (S)-1-(4,4,6,6,6-pentadeutero-5-hydroxyhexyl)-3,7-dimethyl-1H-purine-2,6(3H,7H)-dione. The structural formula is provided in Figure 1 .

Date: 02 November 2018

Figure 1: Structural Formula for PCS499

$$D_3C \xrightarrow{\stackrel{OH}{\downarrow}} D \xrightarrow{O} N \xrightarrow{N} N$$

The molecular formula is C13H15D5N4O3.

The dosage form is a white tablet containing 300 mg of PCS499. The inactive ingredients are hydroxypropylmethylcellulose (HPMC), silicon dioxide, and magnesium stearate.

#### 11.2. Concomitant Medications

At the discretion of the Investigator, over-the-counter (OTC) medications will be allowed for the management of a self-limiting indication (e.g., acetaminophen for headache). The use of concomitant OTC medications, including OTC herbals, must be approved by the Investigator before administration. All prescription medications must be approved by the Investigator throughout the active treatment period.

With the exception of PCS499, investigational drugs are not to be taken during the study.

IMPORTANT: Patients should be instructed to consult with the Investigator before taking any new medication or changing medications and/or dosing regimens throughout the study.

Drugs that are known to be strong inhibitors of CYP1A2 may increase exposure to the investigational product. The Investigator should contact the Medical Monitor prior to (if possible) the initiation of a CYP1A2 inhibiting drug, such as ciprofloxacin, cimetidine, fluvoxamine, etc.

Additional medication limitations are as follows:

- Topical skin treatments to the affected NL area are not permitted during the study.
- Systemic or topical immunosuppressive therapy, including but not limited to corticosteroids (excluding intraarticular injections, inhaled or nasal steroids), calcineurin inhibitors, thalidomide, apremilast, anti-malarials (e.g., hydroxychloroquine, chloroquine), cyclosporine, mycophenolate mofetil, azathioprine, methotrexate, and biologics (TNF-α blockers, anakinra, etc.) are not permitted during the study.

- Oral retinoids are not permitted during the study.
- Phototherapy (UVA/UVB) or photochemotherapy (PUVA) is not permitted during the study.
- Consumption of pentoxifylline, cilostazol, or a theophylline preparation is not permitted during the study.

### 11.3. Treatment Compliance

Patients will be instructed to bring their bottles, whether empty or containing unused study medication, with them for a compliance assessment during each clinic visit. Compliance will be assessed via tablet counts.

### 11.4. Randomization and Blinding

This is an open-label study which does not require a randomization list or blinding.

### 12. STUDY DRUG MATERIALS AND MANAGEMENT

### 12.1. Study Drug

The test article is PCS499 modified release 300mg tablets.

### 12.2. Study Drug Packaging and Labeling

PCS499 tablets will be packaged in high density polyethylene bottles respectively.

Each patient's study medication will be packaged in a study-specific box (kit) and shipped to the study site by a central distribution site.

### 12.3. Study Drug Storage

All investigational drug supplies should be stored in a secure, locked area, under the responsibility of the Investigator or other authorized individual. Study drug must be stored in the original packaging between 20 to 25°C (68 to 77°F), with deviations permitted between 15 to 30°C (59 to 86°F), and protected from extreme conditions of temperature, light, and humidity.

### 12.4. Study Drug Preparation

There is no study drug preparation needed for this study.

#### 12.5. Administration

All patients will take PCS499 300 mg BID with food for 1 week. Beginning at Week 2, patients will commence administration of twice daily dosing of three PCS499 300 mg tablets (900 mg BID) with food. Patients will continue at their assigned dose for the remainder of the study.

Safety and tolerability will be assessed throughout study and the following steps may be taken:

• During the dosing period, if a patient receiving PCS499 900 mg BID experiences unacceptable toxicity (i.e., non-transient, moderate to severe limitation in activity) that is deemed by the Investigator to be related to study drug, his/her dose will be changed to PCS499 600 mg TID with food at the discretion of the Investigator in consultation with the Medical Monitor. If this dose is not tolerated, the dose will be further reduced to PCS499 600 mg BID with food at the discretion of the Investigator in consultation with the Medical Monitor. If 4 out of the first 6 patients dosed in this study require dose modification or discontinue from the study due to a drug-related adverse event within 1 month of dosing, consideration will be made to change the starting dose to 600 mg TID with food for all subsequent patients. If clinically indicated at any time during the study, study medication will be discontinued. However, patients will not be discontinued from the study due to cessation of study drug.

All changes in medication administration will also be noted in the eCRF.

Each kit will be clearly marked with dosage instructions.

Each subject's medication will be packaged for dispensing as described in the study manual.

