## 9.2.2.2. Day 7 and Day 14 (Phone Checks, +/- 1 day)

The site will call the patient on Day 7 and Day 14 to assess for any adverse events or tolerability issues the patient may have experienced since starting dosing. A review of systems will be discussed and any changes in concomitant medications will also be solicited.

- If a patient reports satisfactory tolerability to study medication on the Day 7 Safety Check-in, they will be instructed to increase their morning dose to 3 tablets and their evening dose to 3 tablets.
- If a patient reports tolerability issues, an additional week of dosing with the morning dose of 1 tablet and evening dose of 1 tablet may be performed.
- Patients who are unable to tolerate even the single tablet after 2 weeks of dosing are to be discontinued from the study.

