#### 17.5.1. Adverse Events

Adverse events will be coded using the current version of the Medical Dictionary for Regulatory Activities (MedDRA version 21.0 or higher). The number and percent of patients reporting at least one adverse event will be summarized by System Organ Class (SOC) and Preferred Term (PT) and presented by dose level, severity, relationship to study drug, amount of drug exposure, CONFIDENTIAL

and time. Each patient will contribute only once (i.e., first occurrence) to each of the incidence rates, regardless of the number of occurrences. For reporting of adverse event severity in patients with more than one occurrence of the same adverse event, the patient will only be reported once based on the highest severity of the adverse event observed. Patients who have a serious adverse event (SAE) or who discontinue the study due to an adverse event deemed to be related to study drug will be described in patient narratives.

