#### 19.5.2. Patient Discontinuation

If a patient is discontinued from the study prematurely, the Investigator must select a reason for discontinuation on the termination page (End of Study Phase Status) eCRF. In addition, every effort should be made to complete the assessments listed under the early termination study visit. Patients withdrawn from the study will be considered evaluable for analysis.

A patient may be removed from the study for the following medical or administrative reasons:

- Adverse Event: If a patient experiences an adverse event that the patient finds unacceptable or that, in the judgment of the Principal Investigator, Processa Pharmaceuticals, Inc., or the Medical Monitor presents an unacceptable consequence or risk to the patient, the patient may be discontinued from further participation in the study.
- Administrative Discontinuation: After consultation with the Sponsor or Medical Monitor, a patient may be discontinued from the study for failure to comply with protocol requirements. All instances of noncompliance must be documented in the eCRF.
- Refusal of Treatment: If for any reason the patient refuses treatment during the study, the patient shall be discontinued from the study and the reasons for refusal documented on the eCRF. Reasonable efforts shall be made to monitor the patient for adverse events following such discontinuation. Such efforts shall be documented on the eCRF.

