### 1.2. Study Background/Plan

This is an open-label study that will evaluate the safety of PCS499 for the treatment of necrobiosis lipoidica (NL) and will inform the design of future studies. The study will consist of a 6-month treatment period followed by a 6-month extension period. The test article is PCS499 modified release 300mg tablets.

Approximately 12 NL patients (6-9 patients without ulceration and 3-6 patients with ulceration) who also meet other inclusion/exclusion criteria will be enrolled in the study. Patients will be administered PCS499 900 mg BID. Primary safety and exploratory efficacy analysis will be performed after the last patient completes the 6-month visit. Patients will have the option to continue dosing in an extension period for up to an additional 6 months.

All patients will take PCS499 300 mg BID with food for 1 week beginning at Visit 2/Day 0 (Baseline). At the Visit3/Day 7 and Visit4/Day 14 phone Safety Check-in, patients will be instructed to increase their morning dose to 3 tablets and their evening dose to 3 tablets (PCS499 900 mg BID with food) if satisfactory tolerability to PCS499 300 mg BID is reported. Patients will continue at their assigned dose for the remainder of the study.

During the dosing period, if a patient receiving PCS499 900 mg BID experiences unacceptable toxicity (i.e., non-transient, moderate to severe limitation in activity) that is deemed by the Investigator to be related to study drug, his/her dose will be changed to PCS499 600 mg TID with food at the discretion of the Investigator in consultation with the Medical Monitor. If this dose is not tolerated, the dose will be further reduced to PCS499 600 mg BID with food at the discretion of the Investigator in consultation with the Medical Monitor. If 4 out of the first 6 patients dosed in this study require dose modification or discontinue from the study due to a drug-related adverse event within 1 month of dosing, consideration will be made to change the starting dose to 600 mg TID with food for all subsequent patients. If clinically indicated at any time during the study, study medication will be discontinued. However, patients will not be discontinued from the study due to cessation of study drug. Efficacy and safety data will be collected at regular intervals throughout the course of the study.

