14.2.06.1	Summary of Color and Ulcer Scale Reference Lesion (NLCUS) Results – Modified Intention-to-Treat Population
14.2.06.2	Summary of Color and Ulcer Scale Reference Lesion (NLCUS) Results – Per Protocol Population
14.2.07.1	Summary of Global Assessment Results – Modified Intention-to-Treat Population
14.2.07.2	Summary of Global Assessment Results – Per Protocol Population
14.2.08.1	Summary of Dermatology Life Quality Index Results – Modified Intention-to-Treat Population
14.2.08.2	Summary of Dermatology Life Quality Index Results – Per Protocol Population
14.2.09.1	Summary of Skindex-29 - Dermatology Survey Results – Modified Intention-to-Treat Population
14.2.09.2	Summary of Skindex-29 - Dermatology Survey Results – Per Protocol Population
14.2.10	Summary of Biomarker Results – Biomarker Population
14.3.1.1	Overall Summary of Adverse Events – Safety Population
14.3.1.2	Summary of Treatment Emergent Adverse Events by Body System and Preferred Term – Safety Population
14.3.1.3	Summary of Treatment Emergent Adverse Events by Body System, Preferred Term and Severity – Safety Population
14.3.1.4	Summary of Treatment Emergent Adverse Events by Body System, Preferred Term and Relationship to Study Medication – Safety Population
14.3.1.5	Summary of Adverse Events Leading to Study Discontinuation – Safety Population
14.3.1.6	Summary of Serious Adverse Events – Safety Population
14.3.5.1	Summary of Laboratory Results - Hematology – Safety Population
14.3.5.2	Summary of Laboratory Results - Chemistry – Safety Population

Table Number	Table Title
14.3.5.3	Summary of Laboratory Results - Urinalysis – Safety Population
14.3.6.1	Summary of Vital Signs Results – Safety Population
14.3.6.2	Summary of Electrocardiogram Results – Safety Population

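### Read literally, the 4-of-6 tolerability trigger misses a patient taken straight off study drug for a related adverse event and kept in follow-up; the narratives, one AE table and one listing share the wording

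*Protocol*

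**What the plan says.** **The trigger.** It appears in the Protocol synopsis, 9.1 and 12.5, and in SAP 1.2. It counts patients among the first 6 dosed who "require dose modification or discontinue from the study due to a drug-related adverse event within 1 month of dosing". SAP 1.2 repeats it: "If 4 out of the first 6 patients dosed in this study require dose modification or discontinue from the study". Reaching 4 leads to consideration of 600 mg TID as the starting dose for later patients.

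**Stopping drug is not leaving the study.** Protocol 12.5 allows study medication to be stopped at any time if clinically indicated, and adds: "However, patients will not be discontinued from the study due to cessation of study drug". SAP 1.2 says the same. Protocol 10.3 states: "The intent of this study is to follow all subjects until study termination unless the subject withdraws consent". Protocol 9.2.3.3 provides a separate clinic visit for early discontinuation from study drug.

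**Some sections do take drug stoppers out of the study.**
- Protocol 9.2.2.2, on the 300 mg BID run-in: "Patients who are unable to tolerate even the single tablet after 2 weeks of dosing are to be discontinued from the study".
- Protocol 19.5.2, on refusal: "If for any reason the patient refuses treatment during the study, the patient shall be discontinued from the study".
- Protocol 10.3 and the Adverse Event bullet of 19.5.2 permit, but do not require, withdrawal from the study for an adverse event.

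**Reporting.** Besides SAEs, narratives (synopsis safety analyses and 17.5.1) are required for patients "who discontinue the study due to an adverse event deemed to be related to study drug will be described in patient narratives". SAP Table 14.3.1.5 is titled "Summary of Adverse Events Leading to Study Discontinuation". Listing 16.2.7.2 and the matching listing bullet in SAP 2.9.1 are also defined by discontinuation of the study. By contrast, the overall AE summary in SAP 2.9.1 has one row for TEAEs leading to withdrawal of study drug and another for TEAEs leading to a dose change.

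**The concern.** Safety and tolerability is the primary objective, and this is the protocol's only numeric tolerability rule across patients. Under 12.5, a patient who cannot continue the drug stops it and stays in follow-up. The trigger has no clear place for that patient: the dose was not changed to another dose, and the patient did not leave the study. Two sites with clinically identical patients could report different counts because one kept the patient in follow-up and the other withdrew the patient. The same wording decides who gets a narrative and who appears in the output meant to show treatment-limiting events.

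**Working it through.** The plan gives no error rate or operating characteristic for the trigger, so there is no stated figure to reproduce. The main check is textual.

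**Step 1. Which patients count?** Assume in each case that the cause is a drug-related AE within 1 month.

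| Course | Governing text | Counted as written? |
|---|---|---|
| Switched from 900 mg BID to 600 mg TID, later stopped or not | 12.5 | Yes, dose modification |
| Cannot tolerate 300 mg BID after 2 weeks | 9.2.2.2 | Yes, leaves the study |
| Refuses treatment because of the AE | 19.5.2, Refusal | Yes, leaves the study |
| Withdrawn from the study for the AE | 10.3 or 19.5.2 (optional) | Yes, leaves the study |
| Taken directly off drug, follow-up kept | 12.5 and 10.3 | No, unless dose modification includes stopping |

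No section defines dose modification. Protocol 12.5 describes changing or reducing the dose separately from stopping it, and SAP 2.9.1 gives dose change and drug withdrawal separate rows. Both point towards stopping not being a modification, but neither settles it.

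**Step 2. One patient can decide the count.** Take 3 switches to 600 mg TID, 1 direct stop kept in follow-up, and 2 patients without trouble. As written the count is 3 of 6 and the trigger is not reached. If drug stops count it is 3 + 1 = 4 of 6 and the trigger is reached.

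**Step 3. How often could this matter, given poor tolerability?** Let f of the 6 patients have a related treatment-limiting event, and let each such event independently have chance q of being an uncounted direct stop. The documents give no value for q, so it is an assumption. The counted number is Binomial(f, 1 − q).
- f = 4: P(count ≥ 4) = (1 − q)^4.
- f = 5: P(count ≥ 4) = (1 − q)^5 + 5q(1 − q)^4.

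| q | f = 4 | f = 5 |
|---|---|---|
| 0 | 100% | 100% |
| 10% | 66% | 92% |
| 20% | 41% | 74% |
| 40% | 13% | 34% |

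These are conditional on 4 or 5 of 6 patients having failed. They are not overall probabilities.

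**Step 4. The only rate in the documents.** Protocol 7.3.1 reports nausea in 12 PCS499 patients (13.5%), which implies 12 / 0.135 = 88.9, or about 89 patients. It also reports 6 dose reductions and 4 GI stops. With no overlap that is 10 / 89 = 11.2%, and the chance of 4 or more of 6 is about 0.2%. If all 4 stops followed a reduction, the rate is 6 / 89 = 6.7% and the chance about 0.03%. This compares poorly with the trigger. The events come from a 48-week treatment period at 600 mg BID, whereas the trigger covers 1 month, mostly at 900 mg BID. The longer period makes the figure too high for a 1-month window, and the lower dose may make it too low.

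**Step 5. What reporting is lost?** A non-serious related AE that stops the drug, with follow-up kept, has no required narrative and no row in Table 14.3.1.5 or Listing 16.2.7.2. It is still counted in the overall AE summary and shown in the full AE listing. The action taken with study drug is recorded for every AE (15.2.1), and dosing is summarized by visit (SAP 2.5).

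**The case against.** The strongest reply is that the missed group is narrow. It needs a direct stop, for a related AE, within 1 month, with no step-down first and follow-up kept. For unacceptable toxicity at 900 mg BID, 12.5 names a change to 600 mg TID as the first response, and that patient counts. Protocol 10.3 and 19.5.2 let the site withdraw a patient for an AE, and that patient counts too. Dose modification can also be read to include reduction to zero. Because the trigger only prompts consideration, and the Medical Monitor is already consulted on toxicity dose changes, nobody is bound to the narrow reading. All of this stands and limits the weight of the point. It does not remove the ambiguity, because the same patient is counted or not according to the section followed.

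A reader might infer more than the documents support:
- *That drug stops never count.* They do when a dose change came first or when the patient leaves the study for a related AE.
- *That every refusal counts.* The trigger also requires a drug-related AE, and 10.3 lists the patient's decision as a withdrawal reason separate from an adverse event.
- *That counting a run-in failure is an error.* The rule covers the first 6 patients dosed, and including someone who cannot tolerate 300 mg BID for a related AE is reasonable and cautious.
- *That these events vanish from the report.* Step 5 of the check shows that they do not.
- *That a missed trigger leaves later patients on a higher daily dose.* 900 mg × 2 and 600 mg × 3 are both 1800 mg. Protocol 7.4 does say that the 900 mg dose gave higher AUC and Cmax, so the regimens are not identical in exposure, but each later patient keeps the individual step-down route.

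**Conclusion.** The point holds on the literal wording and is minor. The trigger omits a direct drug stop with follow-up kept, which is the course 12.5 itself prescribes when study drug is stopped, and the narratives, one table and one listing share the omission. One such patient among six can move the count from 4 to 3. The consequence is bounded: at most about 12 − 6 = 6 later patients, a decision that is only considered, and an alternative regimen with the same daily dose.

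No probability that the trigger misfires should be inferred. The conditional figures rest on an assumed q, and the documents give no failure rate for 900 mg BID in necrobiosis lipoidica. At the Phase 2 rate the trigger would almost never be approached, so the wording matters only if tolerability is much worse than that, which is the situation the rule is there to detect.

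**What to change.** 1. **Trigger** (synopsis, 9.1, 12.5, SAP 1.2). After dose modification, replace the limb on leaving the study with *or permanently discontinue study drug or the study*. Keep the drug-related AE condition and the 1-month window.
2. **Reporting** (synopsis safety analyses, 17.5.1, the SAP 2.9.1 listing bullet, Table 14.3.1.5, Listing 16.2.7.2). Use *discontinuation of study drug or study*. Change all five together, or new mismatches appear.
3. **Alignment with 12.5** (9.2.2.2 and the Refusal bullet of 19.5.2). Say that study drug is stopped and the patient stays in follow-up unless consent is withdrawn. Do this only with item 1, because on its own it would move more patients into the uncounted group.

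The cost is a few wording edits, which 23.2 makes a protocol amendment, a matching SAP update, and possibly a few more narratives. No new data are needed, because the action taken with study drug is already collected for each AE and the SAP already counts TEAEs leading to its withdrawal.
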